### **4.3 Exclusion Criteria**

- Patients < 18 years of age
- Presence of a permanent pacemaker, implantable cardiac defibrillator, or cardiac resynchronization therapy
- Unable to tolerate ICM or traditional monitoring with ECG, Holter, or MCOT monitoring
- Unable to tolerate AAD, OAC, and CA as part of AF standard of care
- ICM inserted for cryptogenic stroke or syncope
- Was not followed > 12 months
- CA performed for AF before ICM implant

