## **5 STUDY INTERVENTIONS**

### **5.1 Interventions, Administration, and Duration**

No intervention or administration will be performed due to the observational nature of each phase. Charts of patients enrolled in the study will be reviewed for an initial monitoring method, any changes in

management, including AAD, OAC, CA, as per physicians' preference, arrhythmia recurrence, need for redo CA, and AF-related complication, for 12 months after enrollment. Lastly, the primary outcomes of AF freedom and continued AAD and OAC use will be noted at the end of the study duration.

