## 6 STUDY PROCEDURES

### 6.1 Description of Evaluation

*Table 1. Variables for data collection will include but are not limited to the following.*

Variables	Description and Definition
Age	## Years
Gender	0 = Male, 1 = Female
BMI	## kg/m2
Race	0 = Caucasian, 1 = African American, 2 = Hispanic, 3 = Asian, 4 = Other
Hypertension	0 = No, 1 = Yes
Hyperlipidemia	0 = No, 1 = Yes
Diabetes Mellitus	0 = No, 1 = Yes
Coronary Artery Disease	0 = No, 1 = Yes
CVA/TIA	0 = No, 1 = Yes
Peripheral Artery Disease	0 = No, 1 = Yes
Obstructive Sleep Apnea	0 = No, 1 = Yes
Compensated HF (EF > 35%)	0 = No, 1 = Yes
History of Smoking	0 = No, 1 = Yes
Thyroid Dysfunction	0 = None, 1 = Hypothyroidism, 2 = Hyperthyroidism
Chronic Obstructive Pulmonary Disease	0 = No, 1 = Yes
Gastrointestinal Disorders	0 = No, 1 = Yes
CHADS 2 /VASC 2 Score	##
Antiarrhythmic Drug	
History of Cardioversion	0 = No, 1 = Yes
Baseline AAD Use	0 = No, 1 = Yes
Duration of Arrhythmia	## Mos.
Left Atrial Size	## cm.
Left Ventricular Ejection Fraction	## %
Access to EP	0 = No, 1 = Yes
Compliance to OAC	0 = No, 1 = Yes
Attempted AAD	0 = No, 1 = Yes
Need for Catheter Ablation	0 = No, 1 = Yes
Time to Catheter Ablation	## Days
Number of Monitors used Post-CA	##

Type of Monitors Used	0 = MCOT, 1 = 48-Hr Holter
Need for Redo Ablation	0 = No, 1 = Yes
Time to Redo Ablation	## Days
CV-Related Hospital Duration	## Days
Length of Stay	## Days
AF-Related Hospitalization	0 = No, 1 = Yes
HF-Related Hospitalization	0 = No, 1 = Yes
Bleeding Complication	0 = No, 1 = Yes
Stroke and TIA	0 = No, 1 = Yes
Freedom of AF at 12 Mos.	0 = No, 1 = Yes
Continued OAC Use	0 = No, 1 = Yes
Continued AAD Use	0 = No, 1 = Yes

Abbreviations: BMI – body mass index, CVA = cerebrovascular accident, TIA – transient ischemic attack, AAD = antiarrhythmic drug, CV – cardiovascular, CA = catheter ablation, AF – atrial fibrillation, HF – heart failure, OAC – oral anticoagulation, MCOT – mobile cardiac outpatient telemetry

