## 6.3 Follow-up Visits

Follow-up will occur up to 12 months after enrollment into the study. Follow-up visits and management changes will occur at the treating physician's discretion.

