## 9.3 Outcomes

Primary	Secondary

• Access to care

• Time of AAD initiation

• Time of OAC initiation

• Time to CA

• Any changes or discontinuation of AAD post-ablation

• Any changes or discontinuation of OAC post-ablation

• Arrhythmia recurrence

• Redo Ablation

	

• Systemic thromboembolic events

• All AF and cardiovascular related hospitalization

• Heart failure exacerbations

• Bleeding complications

• Cardiovascular mortality

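### Redo ablation and post-ablation AAD/OAC changes are counted in a window that starts at enrollment, so any difference between arms in CA timing can show up as a difference in these three primary outcomes

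*Combined protocol and SAP*

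**What the plan says.** - Section 9.3 includes among its primary outcomes "Any changes or discontinuation of AAD post-ablation", "Any changes or discontinuation of OAC post-ablation" and "Redo Ablation". Time to CA is another primary outcome in the same list.
- Section 5.1 sets the review window, and names redo procedures within it: "need for redo CA, and AF-related complication, for 12 months after enrollment". Section 6.3 agrees: "Follow-up will occur up to 12 months after enrollment into the study". When CA happens is left to the treating physician.
- Table 1 (Section 6.1) codes "Need for Redo Ablation" as 0/1. It also has time to CA and time to redo ablation in days, with no origin stated for either. It has no field for a post-ablation change of AAD or OAC, only all-patient fields for continued use.
- Section 9.4 gives chi-square for categorical variables as appropriate, Cox models for hazard ratios, and Kaplan-Meier graphs where appropriate. It ties none of these to a named outcome and states no time origin, risk set or censoring rule.
- Section 4.3 excludes a patient who "Was not followed > 12 months". It also excludes CA before ICM implant, a criterion with no stated counterpart for the non-ICM arm.

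**The concern.** A patient ablated at month 3 is watched for nine months after CA, and one ablated at month 7 for five. If one arm is ablated earlier on average, it has more time in which a redo or a drug change can be recorded, even when the risk per month after CA is identical. A real difference in time to CA could then carry over into three other primary outcomes and be read as separate evidence about monitoring.

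There is a second, distinct problem. Patients who reach CA are selected by an event after baseline that the monitoring method may influence. The ablated subsets of the two arms may therefore differ in kind as well as in length of observation.

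**Working it through.** The plan gives no expected redo rate, CA share or CA timing, so it has no figure of its own to reproduce on this point.

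**Inputs from the documents.** Window of 12 months from enrollment (5.1, 6.3); significance level 0.05 (9.4); 1250 patients per arm (9.2).

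**Assumptions.** Redo hazard h after CA is constant and equal in the two arms, at 1% or 2% per month. CA is at month 3 in one arm and month 4, 5, 6 or 7 in the other. 30% of each arm is ablated: 0.30 × 1250 = 375.

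**Step 1: redo recorded in the window.** p = 1 − exp(−h(12 − t)), where t is the month of CA. At h = 0.02:
- t = 3: 1 − exp(−0.18) = 16.5%
- t = 7: 1 − exp(−0.10) = 9.5%
- ratio 1.73, although the hazards are equal

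**Step 2: how often a two-proportion test rejects.** For 3 v 7 at h = 0.02, the pooled proportion is 13.0% and the standard error is √(2 × 0.130 × 0.870 / 375) = 0.0246. The expected z is 0.0696 / 0.0246 = 2.83. The chance of exceeding 1.96 is about Φ(0.87) = 81%; simulation gave 82%.

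| CA month | h = 1%: recorded | False rejection | h = 2%: recorded | False rejection |
|---|---|---|---|---|
| 3 v 4 | 8.6% v 7.7% | 7% | 16.5% v 14.8% | 10% |
| 3 v 5 | 8.6% v 6.8% | 16% | 16.5% v 13.1% | 26% |
| 3 v 6 | 8.6% v 5.8% | 31% | 16.5% v 11.3% | 53% |
| 3 v 7 | 8.6% v 4.9% | 53% | 16.5% v 9.5% | 82% |

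**Step 3: sensitivity of the 3 v 7 case.**
- 200 ablated per arm: 31–55%.
- 125 ablated per arm (10% of 1250): 22–37%.
- Events clustered early (Weibull shape 0.5, 12-month risk 21%, 375 per arm): ratio 1.31 and 37% rejection, against 1.73 and 82% under a constant hazard.

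**Step 4: does a survival method cure it?** Only with the right origin. A separate simulation of 4000 runs assumed 625 ablated per arm, an equal 20% redo risk in the 12 months after CA, and CA times spread two months either side of the arm mean. False rejection was:

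| Analysis | Mean CA 4 v 4 | 3 v 5 | 2 v 6 |
|---|---|---|---|
| Chi-square, enrollment window | 5.0% | 37% | 91% |
| Log-rank timed from enrollment | 5.1% | 41% | 94% |
| Log-rank timed from CA, censored | 5.1% | 5.0% | 5.0% |
| Chi-square, equal 12 months after CA | 4.6% | 5.6% | 4.8% |

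**Step 5: all patients as denominator.** This does not isolate redo risk either. With CA at month 4 in both arms, the same 20% risk, and 60% v 40% ablated, the recorded risk among ablated patients is 1 − 0.8^(8/12) = 13.8%. Over all patients that is 0.6 × 13.8% = 8.3% against 0.4 × 13.8% = 5.5%, ratio 1.50, rejected about 78% of the time with 1250 per arm. The difference reflects how many were ablated, not how often ablation had to be repeated.

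**The case against.** Several points on the other side are sound.

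- **No predicted direction.** A reader might infer that the study expects ICM to bring CA forward, so that the ICM arm will show more redo procedures. The documents do not support this. Section 2.2 hypothesises only that ICM monitoring is superior, Section 9.1 states a null of no difference, and Section 9.2 assumes equal CA use. Nor is the direction of any bias certain. Because the prior-CA exclusion refers only to ICM implant, non-ICM patients ablated before enrollment could be at risk of redo from day 0, which pushes the other way.
- **Chi-square is not fixed as the test.** Section 9.4 qualifies it and also plans Cox and Kaplan-Meier, and Table 1 collects times in days. That stands. However, no origin is given, the only stated window runs from enrollment, and Step 4 shows that a survival analysis timed from enrollment does no better.
- **The drug comparison is largely covered.** Sections 1.1, 3 and 5.1 already name continued AAD and OAC use as primary, and these fields apply to every patient. That stands. Section 9.3 still lists the post-ablation versions as primary, and no Table 1 field records them.
- **Power.** A reader might also infer that the 99% in Section 9.2 is contradicted for the ablated subset. That section names neither an endpoint nor an effect size, so the figure can be neither confirmed nor refuted here.
- **Later data may exist.** The follow-up criterion in Section 4.3 suggests that some charts run past 12 months. The stated review window nevertheless ends at 12.

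**Conclusion.** The concern holds as a structural defect, with high confidence. It goes beyond missing detail, because the enrollment-based window is a stated rule, and applying it gives unequal post-CA observation whenever CA timing differs between arms.

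The size is illustrative. It rests on an assumed equal, constant hazard, assumed CA months and an assumed 30% ablated. It runs from little above nominal (7–10%) for a one-month gap to 53–82% for a four-month gap. The 82% should not be read as the study's false-positive rate: it is one corner of the range, and it falls with early clustering or fewer ablations. With equal CA timing and equal CA use there is no inflation. The calculations concern redo ablation. The same mechanism applies to post-ablation drug changes, but nothing in the documents allows those to be sized.

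**What to change.** In Sections 9.3 and 9.4:

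1. Analyse the three outcomes among ablated patients with time zero at first CA, by Kaplan-Meier and Cox with censoring at the end of chart follow-up. Alternatively, abstract the same fixed post-CA period for every ablated patient. Do not use chi-square on 0/1 values within the enrollment window.
2. In Table 1, define time to redo ablation as days from first CA. State the origin of the existing time-to-CA field, so that post-CA follow-up can be derived from it. Add the date of the first AAD or OAC change after ablation.
3. Label these results as comparisons within ablated patients. Moving the clock to CA removes unequal exposure but not selection into CA.
4. Rest the between-arm drug conclusion on continued AAD and OAC use in all patients, as Sections 1.1, 3 and 5.1 already provide.

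The cost is plan wording, a little more chart abstraction (more if a fixed post-CA period is chosen), and a narrower interpretation of three outcomes. Whether they also move to secondary status is a matter of preference; the correction does not depend on it.

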### **1.2 Secondary Objectives**

- To evaluate differences in catheter ablation (CA) and AAD for rhythm control and AF-related complications in those with and without ICM.

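### The secondary hospitalization outcome does not separate planned ablation stays from unplanned admissions, so a difference in ablation use can pass for a difference in AF complications

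*Combined protocol and SAP*

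**What the plan says.** Section 9.3 gives the outcome as a single line, "All AF and cardiovascular related hospitalization", in the secondary column. The other entries in that column are thromboembolic events, heart failure exacerbations, bleeding and cardiovascular death. The outcome is not defined further, and no section describes an exclusion or adjudication.

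In Table 1 (section 6.1) the matching fields are "AF-Related Hospitalization" and its heart-failure counterpart, both yes/no, and "CV-Related Hospital Duration" and a length of stay, both in days. No listed field holds an admission date, a reason for admission or an elective flag. The table describes its list as open-ended.

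Section 1.2 sets a secondary objective that covers differences in CA use and also "AF-related complications in those with and without ICM". Section 5.1 has charts reviewed for CA, "need for redo CA, and AF-related complication, for 12 months after enrollment". Section 9.3 places time to CA and redo ablation among the primary outcomes.

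**The concern.** The word All, with no field to qualify it, leaves an abstractor no ground for leaving out an overnight stay for elective ablation. Such a stay is AF-related and is a hospitalization. The procedure would then be counted twice: once as treatment, in the primary comparisons of CA timing and redo ablation, and again in an outcome that sits among adverse events and that readers will take as harm.

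This would not matter if both arms ablated equally often, but the design does not secure that. Arms are not randomized, and CA follows physician preference (section 5.1). Section 4.3 excludes patients ablated before an ICM implant but has no parallel wording for patients who never receive an ICM, so the arms may differ in ablation history at entry. Section 9.4 names chi-square tests and Cox models but no covariates.

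Two errors are possible: a false excess of hospitalization in the arm that ablates more, and a real reduction in unplanned admissions that the procedural stays cancel.

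**Working it through.** **The plan's own figure.** There is none for this outcome. Section 9.2 claims 99% power with 2500 patients but attaches it to no endpoint, event rate or effect size. It cannot be reproduced and does not bear on this point.

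**Inputs from the documents.** 1250 patients per arm (section 9.2); significance at p < 0.05 and chi-square for categorical variables (section 9.4); 12-month window (section 5.1).

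**Inputs assumed, because the documents give none.** Unplanned AF/cardiovascular admission u, equal in both arms and independent of CA; CA rates c1 and c0; share f of CAs coded as an admission.

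**Formula.** Recorded event rate = 1 − (1 − u)(1 − f·c). With equal u, the false difference is (1 − u)·f·(c1 − c0). It is zero if c1 = c0 or f = 0. The test is the pooled two-proportion z, with SE = √[p̄(1 − p̄)·2/1250].

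**False difference, u = 15%, CA 40% v 30%:**

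| f | CA 40% arm | CA 30% arm | Difference | SE | z | p (about) |
|---|---|---|---|---|---|---|
| 0.25 | 1 − 0.85×0.90 = 23.5% | 1 − 0.85×0.925 = 21.4% | 2.1 points | 0.0167 | 1.27 | 0.20 |
| 0.5 | 1 − 0.85×0.80 = 32.0% | 1 − 0.85×0.85 = 27.75% | 4.25 points | 0.0183 | 2.32 | 0.02 |
| 1 | 1 − 0.85×0.60 = 49.0% | 1 − 0.85×0.70 = 40.5% | 8.5 points | 0.0199 | 4.27 | 0.00002 |

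**Other CA gaps, same u.** CA 40% v 20%: 0.85 × f × 0.20 = 4.25, 8.5 and 17 points. CA 35% v 30%: 0.85 × f × 0.05 = 1.1, 2.1 and 4.25 points.

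**Probability of a significant result with no true difference** (two-sided 0.05, 1250 per arm), for f = 0.25, 0.5 and 1:

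- u = 20%, CA 30% v 40%: 20%, 56%, 98%
- u = 10%, CA 30% v 40%: 31%, 73%, 99.6%
- u = 20%, CA 30% v 35%: 9%, 19%, 52%
- equal CA rates, or planned stays excluded (f = 0): 5.0%

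**Masking.** Suppose ICM truly lowers unplanned admission from 15% to 10%. Measured cleanly, z = 0.05/0.01323 = 3.78. Now let CA be 40% with ICM and 30% without:

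- f = 0.25: 1 − 0.90×0.90 = 19.0% v 21.4%. The benefit is cut to 2.4 points, z = 0.02375/0.01606 = 1.48.
- f = 0.5: 1 − 0.90×0.80 = 28.0% v 27.75%. The benefit is gone.
- f = 1: 1 − 0.90×0.60 = 46.0% v 40.5%. The direction is reversed.

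**The case against.** The strongest reply is that the protocol nowhere says that ablation stays count. It gives one undefined line and an open-ended list of variables. Section 5.1 names redo CA and AF-related complications as separate items, and section 9.3 puts redo ablation and hospitalization in different columns, which suggests that procedures were not meant to be complications. This stands in part. It shows a likely intent, but no rule carries that intent to abstractors at several centers, and the literal wording runs the other way.

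Second, every rate above is assumed, and section 9.2 assumes equal CA use, under which the bias is nil. With a 5-point CA gap and a quarter of stays coded, the false-positive rate is only 9% (u = 20%). This limits the claim about size. However, the equality in section 9.2 is a power assumption, while section 1.2 sets out to examine differences in CA. A difference in time to CA need not mean a difference in 12-month CA rates.

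Third, total AF and cardiovascular hospitalization is a legitimate measure of resource use, and section 9.3 does not itself call it a complication. This stands, and it is a reason to keep the total alongside the unplanned outcome.

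A reader might also infer that ICM-insertion stays load the ICM arm. The documents do not show this. Insertion may be the index event or may not be an admission, and under the crossover allowed in section 9.1 it is unclear which arm would carry it. Nor do they show that hospital days are inflated: the two duration fields are undefined, and no figure for days can be derived.

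**Conclusion.** The concern holds in conditional form. As written, the outcome mixes planned ablation stays with unplanned admissions, and the listed fields cannot separate them afterwards. That much follows from the text.

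Bias in the comparison needs two further things, neither of which the documents quantify: CA use that differs between arms, and at least some CA stays coded as admissions. With 15% unplanned admission in both arms and CA 40% v 30%, the false difference runs from 2.1 points (not significant) to 8.5 points (highly significant). It disappears with equal CA use. The direction is against whichever arm ablates more; the documents do not establish that this will be the ICM arm. Effects through ICM insertion, mainly in crossovers, and on hospital days are possible but not shown.

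This is a secondary outcome, so the primary comparisons are untouched. The correction is cheap and should be made before abstraction.

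**What to change.** - In section 9.3, make the outcome unplanned AF-related or cardiovascular hospitalization. State that planned stays for CA or redo CA are not events, but that a complication prolonging or following a planned stay still is.
- In Table 1, add a planned/unplanned code, with the procedure where planned, to the hospitalization fields.
- Report total hospitalization and planned procedural hospitalization separately, as resource use, so that the present measure is not lost.

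The cost is somewhat more chart abstraction, since a patient with both kinds of stay needs each one classified and not just a single yes or no. There will be fewer events. Borderline admissions need a short written coding rule. Abstractors may know the monitoring method when they apply it, so the rule should be fixed in advance and should leave little to judgement. Charts are already being reviewed for CA, redo CA and complications, so no new data source is needed.

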## 9.4 Data Analyses

Statistical analysis will be performed on both continuous and categorical variables. As appropriate, continuous variables will be reported as mean  $\pm$  standard deviation and compared with two-tailed T-tests and Mann-Whitney testing. Categorical variables will be reported as frequency and percentages and compared with Chi-square testing as appropriate. Cox proportional regression models will be used for hazard ratios and confidence intervals. A p-value  $< 0.05$  will be used to determine statistical significance. Kaplan-Meier graphs will be calculated when appropriate. We will use SPSS [IBM, Armonk, New York] for all statistical analysis.

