### **2.2 Study Rationale**

Even with its increasing popularity and use, the impact of ICMs on AF management is still being determined and can even be conflicting. Furthermore, the use of ICM is dependent on physician preference. We hypothesize that dynamic monitoring with ICMs is superior to conventional methods and should be used for all patients with AF. Thus, we aim to measure the outcomes of using ICM versus more traditional approaches in patients with AF.

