## **3 STUDY DESIGN**

We propose a multi-center, retrospective study to evaluate the use of ICM versus traditional, non-ICM methods such as ECGs, Holter, and mobile cardiac outpatient telemetry (MCOT) units, referred to as non-ICM from here on out, from 2018 to 2021. The primary outcome will be the evaluation of AF freedom at 12 months with continued AAD and OAC use. Secondary outcomes are described above. This study will be approved by the Institutional Review Board (IRB), and patient consent will not be required due to the nature of the study.

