#### **4.1.2 Consent and Enrollment**

Patients who meet inclusion and exclusion criteria after screening will be directly enrolled in the study. No randomization will occur, but patients will be separated into an ICM and non-ICM arm. We will enroll approximately 2500 patients [n=1250 (ICM) and n=1250 (non-ICM)] from 2018-2021. No consent will be required due to the nature of the study.

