### **4.2 Inclusion Criteria**

- Patients > 18 years of age
- Present for management of AF
- ICM is inserted at the discretion of the treating physician

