## 9 STATISTICAL CONSIDERATIONS

### 9.1 General Design Issues

The null hypothesis is that there is no difference in outcomes between patients who underwent ICM insertion versus more traditional monitoring methods. Patients who start with traditional monitoring can cross into the ICM group at any time throughout the study. Primary and secondary endpoints are described below.

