### **11.2 Participant Confidentiality**

All reports and communications relating to patients in the study will identify each patient only by an investigative site number, the patient's initials, or the patient's study number. The investigator will maintain a patient identification log containing identifying information for each patient enrolled in the study. This document should contain sufficient information and detail to permit the identification of study patients in case follow-up is required. This information should be treated with strict adherence to professional standards of confidentiality and be kept by the investigator under adequate security and restricted access along with other study records.

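### Physicians choose who gets an ICM, yet section 9.4 pre-specifies no adjustment for baseline factors or centre, so baseline differences may be reported as ICM effects.

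*Combined protocol and SAP*

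**What the plan says.** Section 3 describes a "multi-center, retrospective study to evaluate the use of ICM versus traditional, non-ICM methods". The rationale in section 2.2 states that "the use of ICM is dependent on physician preference", and section 4.2 repeats this as a criterion: "ICM is inserted at the discretion of the treating physician". Section 4.1.2 is explicit about allocation: "No randomization will occur, but patients will be separated into an ICM and non-ICM arm". Section 6.2 confirms that there is no randomisation. Section 2.2 also hypothesises that ICM monitoring is superior, so the aim is comparative.

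The whole analysis plan is section 9.4. It names two-tailed t-tests and Mann-Whitney tests for continuous variables. For categorical variables it says: "Categorical variables will be reported as frequency and percentages and compared with Chi-square testing as appropriate". It then adds: "Cox proportional regression models will be used for hazard ratios and confidence intervals". Kaplan-Meier graphs and a 0.05 threshold complete the plan.

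No section names a covariate, propensity score, matching, weighting, stratification factor or centre term. Section 9.2 aims for 1250 patients per arm, which fixes arm sizes but does not balance patient characteristics.

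**The concern.** Physicians who choose between monitoring methods do so with the patient in view. Age, stroke risk, arrhythmia duration, left atrial size, ejection fraction, baseline AAD use and local practice could plausibly influence both that choice and the outcomes: AAD, OAC and ablation use, recurrence, and hospitalisation. If such factors differ between arms, a crude comparison mixes their effect with that of the ICM.

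The two-group tests in section 9.4 cannot adjust for anything. Cox regression can, but no covariates are named, so they would be either omitted or chosen once the data are known. Section 9.4 also does not say which method applies to which outcome. AF freedom at 12 months, continued OAC and continued AAD make up the primary outcome in section 3, and Table 1 codes all three 0/1. No adjusted method for a binary outcome is named.

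What is at stake is the main conclusion. A difference produced by patient selection could be published as a benefit, or a harm, of ICM monitoring. A large sample reduces random error but leaves this bias untouched.

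**Working it through.** **Step 1. The plan's own figure.** Section 9.2 states 99% power with 2500 patients. It gives no event rate, effect size, standard deviation or hazard ratio, so the figure can be neither reproduced nor refuted. Solving backwards (two-sided 5%, 1250 per arm), 99% power corresponds to a difference of about 5.7 points from a 10% rate, 8.5 points from 50%, or 7.5 points from 70%. This point does not depend on the 99%.

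**Step 2. What is collected and what is used.** Table 1 (section 6.1) has 17 variables from age to the stroke-risk score. It also has prior cardioversion, baseline AAD, arrhythmia duration, left atrial size and ejection fraction: 17 + 5 = 22 that read as baseline. None is given a role in the outcome comparison. Centre is not in the table. Section 11.2 mentions a site number only as an identifier, where reports are to "identify each patient only by an investigative site number".

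**Step 3. How large the bias could be.** The documents give no imbalance or event rates, so every input here except n and the 5% level is assumed. Suppose there is no true ICM effect and there are k independent binary factors, each with prevalence q1 in the ICM arm and q0 in the other, and each multiplying risk by R.

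- Arm risk: p = base × (1 + q(R − 1))^k
- Spurious risk ratio: [(1 + q1(R − 1)) / (1 + q0(R − 1))]^k
- Probability of p < 0.05: Φ((d − 1.96·s0)/s1) + Φ((−d − 1.96·s0)/s1), with d = |p1 − p0|, s0 = √(2p̄(1 − p̄)/n), s1 = √((p1(1 − p1) + p0(1 − p0))/n), n = 1250

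Worked case: q1 = 0.50, q0 = 0.30, R = 2, k = 1, base 10%. Then p1 = 0.10 × 1.5 = 0.15, p0 = 0.10 × 1.3 = 0.13, and the spurious ratio is 1.5/1.3 = 1.15. With p̄ = 0.14, s0 = 0.01388 and s1 = 0.01387, so (0.02 − 0.0272)/0.01387 = −0.52 and the probability is 0.302.

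| Prevalence, ICM v non-ICM | R | Factors | Spurious RR | P(p < 0.05), base 10% | base 20% |
|---|---|---|---|---|---|
| 35% v 30% | 1.5 | 1 | 1.02 | 0.054 | 0.060 |
| 35% v 30% | 2 | 1 | 1.04 | 0.066 | 0.087 |
| 40% v 30% | 1.5 | 1 | 1.04 | 0.067 | 0.091 |
| 40% v 30% | 2 | 1 | 1.08 | 0.113 | 0.203 |
| 50% v 30% | 2 | 1 | 1.15 | 0.302 | 0.605 |
| 40% v 30% | 2 | 2 | 1.16 | 0.416 | 0.801 |
| 40% v 30% | 2 | 3 | 1.25 | 0.887 | not possible |

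The last cell is empty because a patient with all three factors would have a risk of 20% × 8 = 160%.

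**Step 4. Sample size does not help.** In the worked case the false-significance rate rises from 30% at 1250 per arm to 53% at 2500 and 82% at 5000.

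**Step 5. What adjustment does.** Individual-level simulation (1500 runs; Monte Carlo standard error at 5% is √(0.05 × 0.95/1500) = 0.006) compared crude with logistic-adjusted rejection:

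| Scenario | Crude | Adjusted |
|---|---|---|
| 40% v 30%, R 1.5, one factor, base 10% | 0.067 | 0.052 |
| 50% v 30%, R 2, one factor, base 10% | 0.309 | 0.054 |
| 50% v 30%, R 2, one factor, base 20% | 0.605 | 0.057 |
| 40% v 30%, R 2, two factors, base 10% | 0.384 | 0.051 |
| 40% v 30%, R 2, three factors, base 10% | 0.878 | 0.064 |

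**Step 6. A second set of assumptions.** Take AF freedom of 70% without a baseline factor and no ICM effect, with 4000 simulated runs. If freedom is 60% with the factor, prevalences of 55% v 45%, 60% v 40% and 65% v 35% give spurious differences of 1, 2 and 3 points and crude rejection of about 8%, 18% and 35%. If freedom is 50% with the factor, the differences are 2, 4 and 6 points and crude rejection is about 17%, 53% and 85%. A Cochran-Mantel-Haenszel test stratified on the factor rejects in about 5% of runs throughout.

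**The case against.** The best defence has five parts.

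- **Restriction.** Section 4.3 excludes other implanted cardiac devices, ICMs placed for cryptogenic stroke or syncope, and ablation before ICM implant. This is real control by design and removes two non-AF reasons for an ICM. It does not balance age, stroke risk, arrhythmia duration, atrial size, ejection fraction or baseline AAD.
- **Cox regression.** It can carry covariates, and several primary outcomes in section 9.3 are times; recurrence, which is close to AF freedom, could also be analysed as a time. The chi-square sentence could be meant partly for baseline tables. For time outcomes the plan is therefore silent on adjustment rather than committed to a crude analysis. That stands, but silence leaves covariates open to choice after the data are seen, and continued OAC and AAD still have no adjusted method.
- **Centre.** Table 1 is open-ended and data are collected by site (section 10.1), so centre could be recorded. What is missing is mainly its analytic role.
- **Magnitude.** It is entirely assumed. A 5-point imbalance in one factor leaves the false-positive rate at 5.4–8.7%. The multi-factor cases let all factors act the same way; opposing factors would partly cancel. The return to about 5% assumes every confounder is measured and modelled. All of this stands, and the figures illustrate a possibility only.
- **Correctability.** The data are retrospective and most covariates are collected, so adjustment could be added at analysis. That is a reason the repair is cheap, not a reason to leave it unspecified.

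**Conclusion.** The concern holds, and the plan should be changed before analysis. Exposure is chosen by the physician, the hypothesis is one of superiority, and section 9.4 specifies only unadjusted two-group tests and Cox models without covariates. That conclusion rests on the text alone.

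The size and direction of any bias are unknown. Under the assumed scenarios the harm runs from negligible (one weak or slightly unbalanced factor) to severe (several factors running the same way, with false significance in up to about 80–89% of studies). Adjustment is necessary but not sufficient: it would not make the comparison equivalent to a randomised one.

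**What to change.** In section 9.4, make the main between-arm analysis of each outcome adjusted, by propensity-score weighting or by covariate-adjusted logistic (binary) and Cox (time-to-event) models, and say which method applies to which outcome.

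1. Define an index date for both arms. State how crossovers are classified, since section 9.1 says: "Patients who start with traditional monitoring can cross into the ICM group at any time throughout the study".
2. Pre-specify the confounders from Table 1 variables measured before that date: age, sex, BMI, race, comorbidities, stroke-risk score, arrhythmia duration, left atrial size, ejection fraction, prior cardioversion and baseline AAD.
3. Record centre as a data item and include it or stratify on it.
4. Keep out anything recorded after the index date, such as Need for Catheter Ablation. Attempted AAD and Compliance to OAC have no timing in Table 1 and should be excluded if they fall after it.
5. Report standardised differences and label crude tests as descriptive.
6. State as limitations unmeasured confounding, crossover, and unequal AF detection between monitoring methods.

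The cost is SAP wording, an index-date definition, one added data item and analysis time; the other covariates are already listed. Weighting loses some precision. With effective size (Σw)²/Σw² and overlap weights, the illustrations keep about 1194 to 1237 of 1250 per arm, a loss of 1% to 4.5% (13/1250 to 56/1250). Stronger real imbalance would cost more.
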